5.1.2 Endpoints

The descriptive analysis of primary and secondary endpoints will be conducted as described in 5.1.

5.3 Efficacy Evaluation

5.3.1 Analysis of Primary Endpoint(s)

The analysis of the primary endpoint is based on the FAS and thus is as close as possible to the ITT principle.

The primary outcome is analysed with a linear mixed effects model with the change from baseline of the PHQ-15 score at 6 weeks and 3 months as dependent variable, treatment group (COV.EXPECT, COV.SUPPORT, and TAU), time (categorical: 6 weeks and 3 months), the stratification variable gender as well as baseline PHQ-15 as fixed effects and patient as random effect. Further, the interaction between time and random group is included and will be excluded from the model if the test result of the interaction is p≥0.05. If the interaction remains in the model, the respective contrast at 3 months will be explored further. If it is removed from the model, the overall treatment effect remains stable over time and can also be interpreted as the effect at the interesting time point 3 months.

The estimation will be performed using Maximum-Likelihood estimation with an AR(1)-structure for residual errors.

For the primary hypothesis, the global treatment effect will be tested first using the F-Test (two-sided). If the p-value is < 0.05, the contrasts in change for COV.EXPECT vs. TAU and COV.SUPPORT vs. TAU at a 5% level (two-sided) will be tested using the Wald test. Because of the closed testing principle an adjustment of the contrast p-values for multiplicity is not necessary. Mean difference estimates together with 95% confidence intervals will be reported.

After final database closure this analysis is repeated with an analogous model that further includes the measurement of the 6 months follow-up. The 3-months estimates from this model will only be interpreted as sensitivity analyses of the primary endpoint analysis.

The assumptions regarding normality of residuals are examined graphically. Histograms and quantile-quantile plots are used to evaluate normality of residuals. In case of unmet assumptions data can be transformed accordingly.

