1.3 Study Endpoint(s)

Primary endpoint:

 Change from baseline in overall somatic symptom severity at 3 months measured with the sum score of the Patient Health Questionnaire 15 (PHQ-15)

Secondary endpoints:

- Change from baseline in overall somatic symptom severity at 6 weeks and 6 months measured with the PHQ-15
- Subjective improvement of Long COVID symptoms (improved vs. stable / worsened) at 6 weeks, 3 months, and 6 months
- Change from baseline in fatigue measured with the Chalder Fatigue Scale (CFS) at 6 weeks, 3 months, and 6 months
- Change from baseline in pain measured with an adapted version of the Pain Disability Index (PDI) at 6 weeks, 3 months, and 6 months

Version 1.0 Page 7 of 18

- Post-exertional malaise measured with the DePaul Symptom Questionnaire Post-Exertional Malaise (DSQ-PEM) at 6 weeks, 3 months, and 6 months
- Change from baseline in long COVID symptoms measured with the Patient Health Questionnaire-15 Post-Acute Infection Syndromes (PHQ-15 PAIS) at 6 weeks, 3 months, and 6 months
- Somatic symptom disorder evaluated with the Structured Clinical Interview for the Diagnostic and Statistical Manual of Mental Disorders, Fifth Edition (DSM-5) (SCID-5) at 3 months
- Change from baseline in symptom perception measured with the Brief Illness Perception Questionnaire (B-IPQ) at 3 months and 6 months

Mediator variables (all variables are measured at BL, 6 weeks, 3 and 6 months):

- Illness-related anxiety measured with the Somatic Symptom Disorder B Criteria Scale (SSD-12)
- Treatment expectations measured with the Treatment Expectation Questionnaire (TEX-Q)
- Expectation of symptom severity, of symptom burden, and of coping with symptoms measured with the European Network to improve diagnostic, treatment and health care for patients with persistent somatic symptoms (EURONET SOMA) Numeric Rating Scales (NRS)

Version 1.0 Page 8 of 18

2 Study Methods

In this chapter, a summary of the basic study methods is provided.

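### Dropping the group-by-time interaction at p≥0.05 lets the data decide whether the primary result is the 3-month effect or a 6-week/3-month average

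*SAP*

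**What the plan says.** SAP section 1.3 names one primary endpoint: "Change from baseline in overall somatic symptom severity at 3 months measured with the sum score" of the PHQ-15. The earlier visit is secondary: "Change from baseline in overall somatic symptom severity at 6 weeks and 6 months measured with the PHQ-15". Section 2.3 sizes the trial on d=0.5 for COV.EXPECT against TAU at 3 months.

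Section 5.3.1 models both visits, with "change from baseline of the PHQ-15 score at 6 weeks and 3 months as dependent variable". The group-by-time interaction starts in the model but "will be excluded from the model if the test result of the interaction is p≥0.05". After removal, the SAP states that "the overall treatment effect remains stable over time and can also be interpreted as the effect at the interesting time point 3 months". The visit-specific route exists only on the other branch: "If the interaction remains in the model, the respective contrast at 3 months will be explored further".

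A global F-test at 5% precedes the COV.EXPECT–TAU and COV.SUPPORT–TAU contrasts, which are left unadjusted by appeal to closed testing. Section 5.3.2 analyses the continuous secondary endpoints in the same manner as the primary one. No other section restores the 3-month contrast once the interaction has gone.

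**The concern.** The rule treats failure to reject as proof of equality. The interaction test is one the trial was not sized for, so p≥0.05 is a likely result even when the effect at 3 months differs materially from that at 6 weeks. Which quantity is reported as the primary result therefore depends on the trial's own data, and the confidence interval is computed as if that had been fixed in advance.

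The SAP itself gives reason not to presume stability. Section 2.5 labels 6 weeks as intermediate and 3 months as post-interventional, and the mediation analysis in section 5.3.4 has mediators at 6 weeks acting on PHQ-15 at 3 months.

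At stake are the size of the headline estimate, the coverage of its interval, and the chance of declaring a 3-month benefit on the strength of an early effect that has faded.

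Two related gaps follow. First, when the interaction is kept, section 5.3.1 does not say which hypothesis the global F-test addresses: equality at 3 months, equality of visit averages or, under reference coding, equality at 6 weeks. Closed testing protects the two 3-month contrasts only in the first case. Second, for the continuous secondary endpoints the between-group difference is also forced to be equal across visits whenever the interaction is dropped.

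**Working it through.** **Inputs from the SAP.** d=0.5 at 3 months, two-sided 5%, 80% power, 64 per arm, 25% loss, 1:1:1 allocation (sections 2.2 and 2.3); the interaction rule and the F-gate (section 5.3.1).

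**Assumptions, not in the SAP.** SD 1 at each visit, correlation r=0.5 or 0.7 between the two change scores, COV.SUPPORT effect half that of COV.EXPECT, complete data on 64 per arm, no covariates, and the 6-week effects listed below.

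**The plan's own figure.** The noncentral t-test with d=0.5 gives power 79.5% at 63 per arm and 80.1% at 64. Inflation: 64/0.75 = 85.3, rounded up to 86, and 86 × 3 = 258. The sample size is reproduced.

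**How often the interaction is dropped.** Test the 3-month minus 6-week difference, whose variance is 2(1−r), on (2, 189) df. Let δ be each arm's true difference between visits. The noncentrality is λ = 64 × Σ(δ − mean δ)² / [2(1−r)].

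With COV.EXPECT at 0.25 then 0.50, δ = (0, 0.25, 0.125) for TAU, COV.EXPECT and COV.SUPPORT. The mean is 0.125, and the sum of squares is 0.125² + 0.125² + 0 = 0.03125.

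- r=0.5: λ = 64 × 0.03125 / 1.0 = 2.0, so P(p≥0.05) = 78%.
- r=0.7: λ = 64 × 0.03125 / 0.6 = 3.33, so P(p≥0.05) = 65%.

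For an 80% chance of keeping the interaction, the COV.EXPECT effect would have to differ between visits by 0.55 SD (r=0.5) or 0.43 SD (r=0.7).

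**What is reported after dropping.** With complete data and equal variances, the pooled effect is the mean of the two visits: (0.25 + 0.50)/2 = 0.375, which is 25% below the true 0.50. More missing data at 3 months would shift it further towards 6 weeks.

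**The whole rule, simulated** (100,000 trials per case: interaction test, F-gate, COV.EXPECT–TAU contrast). Each cell gives r=0.5 / r=0.7. When the interaction is dropped, the gate is the pooled F-test; when it is kept, three readings of the gate are shown. The last column is a fixed 3-month contrast behind a 3-month F-gate.

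| True effect, 6 weeks → 3 months | Dropped, % | Mean if dropped | Mean overall | Coverage, % | Declared, visit-average gate, % | Declared, 3-month gate, % | Declared, 6-week gate, % | Declared, fixed 3-month, % |
|---|---|---|---|---|---|---|---|---|
| 0.25 → 0.50 | 78 / 65 | 0.375 / 0.375 | 0.43 / 0.44 | 88 / 90 | 56 / 51 | 63 / 62 | 46 / 37 | 70 / 70 |
| 0.375 → 0.50 | 91 / 88 | 0.44 / 0.44 | 0.45 / 0.46 | 93 / 93 | 71 / 65 | 72 / 67 | 67 / 60 | 70 / 70 |
| 0.50 → 0.50 | 95 / 95 | 0.50 / 0.50 | 0.50 / 0.50 | 95 / 95 | 82 / 77 | 82 / 77 | 81 / 76 | 70 / 70 |
| 0.375 → 0 (benefit declared) | 55 / 32 | 0.19 / 0.19 | 0.07 / 0.04 | 85 / 90 | 8 / 5 | 8 / 5 | 8 / 5 | 1.3 / 1.2 |

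Without any gate, the fixed 3-month contrast has 80% power at 0.50, as planned.

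**Interval width.** The pooled standard error is √[(1+r)/2] times that of the 3-month contrast: 0.87 at r=0.5 and 0.92 at r=0.7. If effects are constant, keeping the interaction therefore widens the CI by a factor of 1/0.87 = 1.15 or 1/0.92 = 1.09.

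**The case against.** The strongest defence is that the effects may really be similar. The three sessions are 2 weeks apart and the booster comes only after 3 months (section 3.2), so 6 weeks and 3 months could show much the same benefit. In that case the rule is unbiased, covers at 95%, and gains 7–12 points of gated power. With a modest difference (0.375 then 0.50) the harm is small: coverage is 93%, and power lies on either side of the fixed analysis depending on r and the gate. No figure in the SAP fixes the 6-week effect or the correlation. All of this stands, and it limits the size of the point. It does not justify the rule, because the SAP cannot know which case holds and its test cannot tell.

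Several stronger readings are not supported:

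- A reader might infer that the 3-month endpoint is usually replaced. That depends on the assumptions: with no effect at 6 weeks and 0.50 at 3 months, the interaction is dropped in only 29% (r=0.5) or 9% (r=0.7) of trials.
- A reader might count an effect fading from 0.50 to 0.25 as producing false claims. The 3-month effect there is not zero, so a rejection is correct, although the estimate is inflated. Only the zero-effect case measures false claims.
- A reader might quote a single power loss, or a family-wise error of about 9%. Both depend on the gate; the 9% needs a 6-week gate under reference coding, and the SAP states no coding.
- A reader might say that the secondary results collapse to one number. Section 5.3.2 still presents mean changes by visit; only the between-group difference is constrained.
- Adding baseline-by-time may look like part of the remedy, but no error has been shown that it would correct.

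**Conclusion.** The concern holds in conditional form. Section 5.3.1 lets a significance test decide whether the primary estimate is the stated endpoint or an average with a secondary one, then labels both as the 3-month effect. When the visit effects differ, the estimate is pulled towards the 6-week value, upwards or downwards; when they are equal, there is no bias.

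Under the assumptions listed, a 6-week effect half the size of the 3-month effect leads to an overall mean of 0.43–0.44 for a true 0.50, and to gated power of about 37–63% according to the gate, against 70%. An early effect of 0.375 that has vanished by 3 months is declared a 3-month benefit in about 5–8% of trials, against about 1.3%. These figures illustrate the mechanism; they do not predict this trial.

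The undefined gate is a second, smaller fault in the same section. The sample size is correct and unaffected. Because the rule determines the headline result, it should be changed before the analysis.

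**What to change.** In section 5.3.1:

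1. Delete the exclusion rule and the sentence that interprets the reduced model. Keep group-by-time whatever its p-value.
2. Define the primary estimates and tests as the COV.EXPECT–TAU and COV.SUPPORT–TAU contrasts at 3 months from that model.
3. Define the gate as the 2-df test that all three arms are equal at 3 months, so that the closed-testing argument applies to those contrasts.
4. Report the pooled effect, if wanted, as secondary.

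In section 5.3.2, take the visit-specific contrasts for the continuous secondary endpoints from the same full model. Apply the same rule to the later model that adds 6 months, so that its 3-month estimate is specific to that visit.

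The change is one of wording and leaves N=258 as it is. It has a real statistical price: if the effect is constant over the two visits, the CI is about 9–15% wider under the assumed correlations, and gated power is about 70% instead of 77–82%. The ungated 3-month contrast keeps the planned 80%; the gap to 70% comes from the F-gate when COV.SUPPORT has half the effect.

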2.3 Sample Size

The trial is powered for the comparison between the COV.EXPECT group and the TAU group. The type one error (alpha) is not adjusted for multiplicity due to the closed testing principle. A between-group effect size of d=0.5 is expected between COV.EXPECT and TAU for the change from baseline in the PHQ-15 score at 3 months. To detect this effect with a power of 80% and using a two-sided alpha of 5%, 64 patients in each group will be required, resulting in a total sample size of N=192. Assuming a loss to follow-up between baseline and 3 months (time point for primary outcome) of 25%, this results in N=258 randomised patients. Assuming that 50% of the screened patients meet the inclusion criteria, a total of N=516 patients will be assessed for eligibility.

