3.1 Confidence Intervals and P Values

For the primary analysis, the significance level is α =0.05 (two-sided). All further analyses are exploratory and will not be adjusted for multiplicity. All applicable statistical tests will be two-sided. All reported confidence intervals (CI) are at 95% level and two-sided.

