5.3.6 Subgroup Analyses

The analysis of the subgroups is based on the FAS and thus is as close as possible to the ITT principle. Missing values are not imputed, but the implicit MAR assumption of the analysis model will be used.

Exploratory subgroup analyses will be performed for the primary endpoint by the appropriate interaction tests within the linear mixed regression model used within the primary analysis. The presented p-values are of descriptive nature only (two-sided tests). Relevant subgroups will be identified with a p-value for the interaction < 0.15 (EMA, 2019).

Predefined subgroups are:

- Age (young [≤first tercile] vs. middle aged vs. old [>third tercile])
- Gender (male vs. female)
- Education (≤ 10 years in school vs. > 10 years in school)
- Social support (number of people living in household ≤ 1 vs. > 1)
- Duration of Long COVID (< 1 year vs. ≤ 2 years vs. > 2 years)
- Severity of overall somatic symptoms at baseline (PHQ-15 score minimal/mild/moderate 0-14 vs. severe 15-30)
- Any chronic physical disease (SCQ-D)
- Any chronic mental illness (SCQ-D)
- Depression (PHQ-9 <10 vs. ≥10)
- Anxiety (GAD-7 <10 vs. ≥10)
- Biopsychosocial understanding of disease (yes vs. no; open question B-IPQ)
- Source of recruitment (University Medical Centre Hamburg-Eppendorf vs. Self-help group vs. Social media vs. Medical or physiotherapy practice vs. Other)
- Illness-related anxiety (SSD-12 < 24 vs. ≥ 24)
- Treatment expectations (TEX-Q <5 vs. ≥5)
- Alexithymia (TAS-20 <60 vs. ≥ 61)
- Emotion regulation (ERQ suppression split at median)

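### The primary model drops group-by-time when its test gives p≥0.05, and the pooled 6-week/3-month effect is then reported as the 3-month effect

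*SAP*

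**What the plan says.** Section 1.3 defines the primary endpoint as the change in PHQ-15 sum score from baseline to 3 months. Section 2.3 sizes the trial for the same time point: "A between-group effect size of d=0.5 is expected between COV.EXPECT and TAU for the change from baseline in the PHQ-15 score at 3 months". The 6-week PHQ-15 change is a separate secondary endpoint, and Section 2.5 labels 6 weeks as intermediate and 3 months as post-interventional.

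The primary model in Section 5.3.1 takes the changes at 6 weeks and 3 months as joint outcomes, with group, time, gender, baseline PHQ-15 and group-by-time. The interaction term "will be excluded from the model if the test result of the interaction is p≥0.05". If it stays, the 3-month contrast is used. If it goes, the plan holds that "the overall treatment effect remains stable over time and can also be interpreted as the effect at the interesting time point 3 months". A global F-test comes next, followed by the two Wald contrasts against TAU, each reported with a 95% CI.

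Nothing else in the SAP requires the 3-month contrast in every case. The later model with 6-month data is analogous and serves only as a sensitivity analysis. The per-protocol and imputation analyses repeat the primary analysis. Continuous secondary endpoints follow the same model, and subgroups use "interaction tests within the linear mixed regression model used within the primary analysis".

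**The concern.** A significance test on the trial's own data decides which quantity the confirmatory analysis estimates. With the interaction removed, the treatment coefficient is a common effect over both visits. That equals the 3-month effect only if the effect is the same at 6 weeks, and p≥0.05 does not establish this. The final standard error and interval also ignore the preliminary test.

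The error can go either way. An effect still building at 6 weeks is diluted. An effect that has faded by 3 months can be declared present at 3 months. Once the term is dropped, the model's group differences for the primary endpoint (3 months) and the secondary endpoint (6 weeks) are the same number.

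**Working it through.** **The plan's own figure.** A two-sample t-test with d=0.5, two-sided α=0.05 and 80% power needs 63.77, so 64 per arm; power at 64 is 80.1%. With 25% loss, 64/0.75 = 85.3, so 86 per arm and 3×86 = 258. Section 2.3 is reproduced, and it describes one comparison at 3 months with no gain from the 6-week visit.

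**Assumptions.** Three arms of 64 with both visits observed; SD 1 at each visit; correlation r between visits of 0.5 to 0.8. The SAP gives neither r nor the course of the effect. Where the interaction is kept, the global F-test is taken at 3 months. Effects are in SD units, 6 weeks then 3 months.

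**Step 1: how often the term is dropped.** The interaction test is a one-way ANOVA (2 and 189 df) on the visit difference, which has variance 2(1−r). Its noncentrality is λ = 64·Σ(δᵢ−δ̄)²/[2(1−r)], where δᵢ is arm i's change in effect between visits.

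- Growing effect: COV.EXPECT 0.25 then 0.50, COV.SUPPORT half of that. δ = (0, 0.125, 0.25), so Σ(δᵢ−δ̄)² = 0.03125 and 64×0.03125 = 2.0. At r=0.6, λ = 2.0/0.8 = 2.5 and the term is dropped with probability 0.73.
- Transient effect: COV.EXPECT 0.3 then 0, COV.SUPPORT 0. Σ(δᵢ−δ̄)² = 0.06 and 64×0.06 = 3.84. At r=0.6, λ = 3.84/0.8 = 4.8 and the probability is 0.52.

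**Step 2: what is reported after dropping.** With complete data it is the two-visit average. For the growing effect this is (0.25+0.50)/2 = 0.375, a bias of −0.125. The contrast SE is √[(1+r)/64] = 0.158 at r=0.6, so the shift is 0.125/0.158 = 0.79 SE. Coverage of the true 0.50 is then Φ(1.96−0.79) + Φ(1.96+0.79) − 1 ≈ 0.88 within this branch.

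The other branch is not unbiased either. The overall mean estimate at r=0.6 is 0.50−0.065 = 0.435, so the mean when the term is kept is (0.435 − 0.727×0.375)/0.273 ≈ 0.59. The test keeps the term when the observed growth happens to be large.

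**Step 3: the whole procedure, by simulation.**

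| Scenario | r=0.5 | 0.6 | 0.7 | 0.8 | Interaction always kept |
|---|---|---|---|---|---|
| Growing effect: term dropped | 78% | 73% | 65% | 50% | – |
| Transient 0.3 then 0: term dropped | 60% | 52% | 39% | 22% | – |
| Transient 0.3 then 0: overall coverage | 88% | 89% | 91% | 93% | 95% |
| Transient 0.3 then 0: false 3-month claim | 7.4% | 6.4% | 5.5% | 3.7% | about 2.5% |
| Transient 0.4 then 0: false 3-month claim | 8.3% | 6.1% | 4.2% | 3.0% | about 2.5% |
| Stable 0.5, COV.SUPPORT 0.25: gated power | 82% | 79% | 77% | 75% | about 70% |

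For the growing effect, overall coverage is 88-92% and gated power 62-64%, against about 70% with the interaction always kept. Gated power means that both the global F-test and the COV.EXPECT contrast are significant. False claims also have to pass both tests.

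**Step 4: dropout.** Section 2.3 expects 25% loss by 3 months, so some patients will probably have 6-week data only. With 11 such patients per arm (assumed) and r=0.6, each visit has information 64×(1−0.6)/(1−0.36) = 40 on the common effect, and the extra patients add 11 at 6 weeks. The 6-week weight is (40+11)/(80+11) = 0.56. The estimate then leans away from the primary time point. For 0.3 then 0, false claims run from 9.8% (r=0.5) to 4.4% (r=0.8), with coverage of 85-92%.

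**The case against.** The strongest reply is that the harm is conditional. If the effect is the same at both visits, the rule is essentially unbiased, coverage is about 94.5-95%, and gated power is 5-12 points higher than with the fix. The three sessions are two weeks apart, so similar effects at 6 weeks and 3 months are plausible. Under mild growth (0.4 then 0.5) coverage stays at 93-94%, and the rule still has more gated power at r of 0.5 to 0.6. The false-claim rate passes 5% only at lower or moderate correlations; at r=0.8 the interaction test catches most fading effects. The rule is prespecified and leaves the analyst no discretion. Descriptive summaries by visit would probably reveal a strong fade. The simulations also leave out covariate adjustment and the AR(1) structure.

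These points are correct and they limit the size. They do not defend the inference. Constancy is what the preliminary test cannot establish, and the SAP offers no other argument for it. Prespecifying the rule does not correct its bias, and descriptive tables do not repair a confirmatory estimate. The subgroup consequence is minor, because Section 5.3.6 makes those analyses exploratory.

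**Conclusion.** The concern holds and should be corrected before the primary analysis, because the rule governs the trial's only confirmatory estimate, p-value and interval. If the effect doubles between visits, the overall bias is about −0.06 to −0.07 SD at r of 0.5 to 0.7 (−0.125 when the term is dropped), coverage is 88-92%, and about 6 to 8 points of gated power are lost. If the effect is transient, false 3-month claims reach about 8% at r=0.5 with complete data and about 10% with 6-week-only dropouts, and fall below 5% at r=0.8. All of this rests on the assumed correlation and effect courses, so the figures illustrate the rule and do not predict this trial's results. With a constant effect there is no material bias or loss of coverage.

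**What to change.** In Section 5.3.1, keep group-by-time in the primary model whatever its p-value. Define the primary result as the COV.EXPECT vs TAU and COV.SUPPORT vs TAU contrasts at 3 months from that model, and state that the global F-test is also taken at 3 months. Delete the exclusion rule and the sentence that reads the pooled effect as the 3-month effect. Report the interaction p-value descriptively, and label any time-averaged effect as supportive. Carry the same model into Section 5.3.2, and in Section 5.3.6 read subgroup interactions from the 3-month contrast.

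The change is to SAP wording only. In the complete-data simulations it brings bias to about zero and coverage to 94.8-95.2%. The 3-month contrast alone keeps the 80% power of Section 2.3, so no extra patients are needed relative to that calculation. The cost arises if the effect really is constant: the 3-month SE is √[2/(1+r)] times that of the average, about 12% larger at r=0.6, and 5-12 points of gated power are given up. Section 2.3 did not count on that gain.

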2.5 Timing of Analyses

Information on the outcomes are collected at baseline, 6 weeks (intermediate), 3 months (post-interventional), and 6 months (follow-up) after baseline.

The analysis will be conducted at two time points. First it will be conducted after all 3-month follow-up visits are conduced (3 months after randomisation of last patient) and after the database has been reviewed for completeness and accuracy. A soft database lock will be conducted.

The final statistical analysis of the study on all primary and secondary endpoints will be conducted after final database lock and data cleaning at the end of study, i.e. when all data from all subjects have been collected, checked for quality and released for analysis. This is scheduled at about 2 years after recruitment of the first patient.

Version 1.0 Page 9 of 18

3 Statistical Principles

In this chapter, the basic statistical principles for the analyses are summarised.

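### With only two visits, the primary model's patient random effect and AR(1) residuals are redundant: the covariance parameters cannot be separated, no fallback is named, and equal variances are still imposed

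*SAP*

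**What the plan says.** Section 5.3.1 takes "change from baseline of the PHQ-15 score at 6 weeks and 3 months as dependent variable". Time is categorical with those two levels. Because the outcome is a change score, baseline is a covariate and not a third repeated measure. The list of model terms ends with "baseline PHQ-15 as fixed effects and patient as random effect", and the next paragraph adds: "The estimation will be performed using Maximum-Likelihood estimation with an AR(1)-structure for residual errors". A global F-test comes first, followed by Wald tests of each intervention against TAU.

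The 6-month visit is not in this model. After final database closure the analysis is "repeated with an analogous model that further includes the measurement of the 6 months follow-up", and the 3-month estimates from that fit count only as a sensitivity analysis. Section 2.5 gives the assessment times as "baseline, 6 weeks (intermediate), 3 months (post-interventional), and 6 months (follow-up) after baseline".

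Section 5.3.2 analyses the continuous secondary endpoints in the same way. Section 5.8 allows Stata, SAS or R. Section 5.3.1 states no alternative covariance structure for a fit that fails or is singular, and no degrees-of-freedom method for the F-test or the contrasts.

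**The concern.** A patient random intercept and an AR(1) residual process are two ways of describing the same thing, the correlation between a patient's visits. With many visits the data can tell them apart. With two visits there is a single within-patient covariance, and both terms compete to explain it.

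This is the confirmatory model. If the program reports a singular or non-converged fit, someone has to decide what to do after the data are available, without guidance from the SAP, and the three permitted packages may not behave alike. Degrees-of-freedom methods that use the information matrix of the variance parameters would rest on a singular matrix, and the SAP does not say which method the F-test uses.

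The redundant parameter also hides a restriction. The specification looks rich, but it still forces the variance of the change score to be equal at 6 weeks and 3 months. If it is not, the standard error of the 3-month contrast, which is the primary one when the interaction is kept, is wrong.

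**Working it through.** **Inputs from the SAP.** Two post-baseline visits, a patient random effect (read as a random intercept with variance τ²), and AR(1) residuals with variance σ² and correlation ρ (section 5.3.1). From section 2.3: d = 0.5, 80% power, two-sided 5%, 64 per group, 25% loss to follow-up, 258 randomised.

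**The plan's own figure.** For d = 0.5 a two-sample t-test needs 63.77, rounded up to 64 per group (power 80.1%). Then 64/0.75 = 85.3, rounded up to 86 per arm, and 3 × 86 = 258. The sample size reproduces and is not in dispute.

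**Identifiability, two visits.**

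- Variance at each visit: τ² + σ²
- Covariance between visits: τ² + ρσ²

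These are two equations for three unknowns. Three examples:

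| τ² | σ² | ρ | Variance | Covariance |
|---|---|---|---|---|
| 10 | 8 | 0.25 | 10 + 8 = 18 | 10 + 2 = 12 |
| 4 | 14 | 0.571 | 4 + 14 = 18 | 4 + 8 = 12 |
| 0 | 18 | 0.667 | 0 + 18 = 18 | 0 + 12 = 12 |

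The matrix of derivatives of the covariance entries with respect to (τ², σ², ρ) has rank 2 of 3 with two visits and rank 3 of 3 with three. More patients do not help, and a patient seen once informs only τ² + σ².

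**What happens to the treatment effect.** One data set was simulated with assumed values: N = 258, residual SD 4, within-patient correlation 0.6, and 15% and 25% missing at 6 weeks and 3 months. The likelihood was evaluated along the flat direction:

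| ρ | τ² | σ² | Log-likelihood | 3-month contrast | SE |
|---|---|---|---|---|---|
| −0.5 | 13.15 | 4.79 | −1134.844902 | −2.057654 | 0.725649 |
| 0 | 10.75 | 7.18 | −1134.844902 | −2.057654 | 0.725649 |
| 0.4 | 5.96 | 11.97 | −1134.844902 | −2.057654 | 0.725649 |
| 0.6 | 0 | 17.94 | −1134.844902 | −2.057654 | 0.725649 |

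Four optimiser starts ended at four different parameter sets, with contrast and SE agreeing to about four decimals. The row ρ = 0 is the random intercept alone and the row τ² = 0 is AR(1) alone. They are the same marginal model.

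**Equal-variance restriction.** The SAP gives no SDs by visit, so these are assumptions. With complete data and the interaction retained, the model uses the average of the two visit variances for the 3-month contrast.

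- Ratio of reported to true SE: r = √[(s₁² + s₂²)/2] / s₂, where s₁ and s₂ are the SDs at 6 weeks and 3 months
- Type I error: 2 × [1 − Φ(1.96 r)]

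| s₁ | s₂ | Average variance | r | Type I error |
|---|---|---|---|---|
| 3.5 | 4.5 | (12.25 + 20.25)/2 = 16.25 | 4.031/4.5 = 0.896 | 7.9% |
| 3.8 | 4.2 | (14.44 + 17.64)/2 = 16.04 | 4.005/4.2 = 0.954 | 6.2% |
| 4.5 | 3.5 | 16.25 | 4.031/3.5 = 1.152 | 2.4% |

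The error can go either way. These figures are for a single contrast and ignore the global F-test in front of it. If the interaction is dropped, the effect is an average over both visits. With complete data its variance depends only on the average variance and the covariance, so the restriction does no harm there.

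**Later three-visit model.** It is identified. AR(1) by visit order gives the same correlation to the gap from 6 weeks to 3 months (about 13 − 6 = 7 weeks) and the gap from 3 to 6 months (about 13 weeks).

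**The case against.** A reader might infer that the primary analysis cannot be run as written, or that its result would be arbitrary. The check does not support that. Only the split of the covariance is undetermined, and the SAP never says it will report or test that split. The marginal covariance, the contrasts and their model-based standard errors are determined. Nor does a forced repair open much room for choice: if the within-patient correlation is positive, dropping either term gives the same answer.

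The wording also allows a milder reading. If the patient term only names the unit within which AR(1) residuals are correlated, the two-visit model is identified. But the SAP lists the two terms separately, and a literal coding would include both.

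It is also tempting to add that maximum likelihood with a Wald test inflates the type I error to 5.6–5.7%. That takes a normal reference distribution and N = 192. The SAP does not say the Wald test is referred to a normal distribution, and the FAS is built on the randomised patients (258 planned), for which the same formula gives 5.4–5.5%. It supports stating a df method and is not a separate defect.

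Finally, the visit-spacing point concerns a fit whose 3-month estimates are only a sensitivity analysis. That is right, and it carries little weight here.

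What stands after all this: the literal specification is over-parameterised, it has no stated fallback or df method, and it imposes equal variances that the trial has no need to assume.

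**Conclusion.** The point holds as a specification flaw of moderate severity. Taken literally, section 5.3.1 asks two visits to identify three covariance parameters when they can identify two. This alone neither blocks nor biases the primary treatment estimate. The practical risks are a singular Hessian or convergence warning that the SAP does not provide for, and unreliable degrees of freedom under any method that uses the variance-parameter information matrix.

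The possible numerical consequence comes from the equal-variance restriction, which the redundant term does nothing to relax. It amounts to a type I error of about 6% to 8% for the 3-month contrast under the two assumed patterns with larger variance at 3 months, and a conservative test if the variance is smaller there. It is nil if the variances are equal. These figures rest on assumed SDs, complete data and a retained interaction. The identifiability result needs none of those and depends only on reading the patient term as a random intercept added to the AR(1) residuals.

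**What to change.** In section 5.3.1, replace the patient random effect and AR(1) residuals by a single unstructured residual covariance across visits within patient. Fit it by REML with Kenward-Roger degrees of freedom for the F-test and the contrasts. Use the same for the later three-visit model, where it also removes the equal-spacing assumption, and for the continuous secondary endpoints that follow the primary model. State what will be done if the fit does not converge.

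Minimum fix: keep only one of the two terms and state the degrees-of-freedom method. This removes the redundancy but keeps the equal-variance restriction.

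Cost: a sentence or two of SAP text and a line of code. Unstructured needs three covariance parameters at two visits, one more than either identified two-parameter model, and six at three visits. No further data are needed and the sample size does not change. The change should be made before the primary analysis is run.
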